3.2.2 Secondary Endpoints

- Improvement in esophageal pH exposure.
- Cessation or decreased in use of anti-reflux medication
- Determination of gastric dysmotility as a contributory factor in GERD after SG
- Objective improvement or resolution of esophagitis utilizing LA classification.

3.2.3 Inclusion Criteria

Participants will be men and women between the ages of 18 and 80 who have undergone sleeve gastrectomyat least 6 months prior to enrollment as treatment of morbid obesity and who have one or more of the following:

- 1. Symptomatic reflux: (heartburn, chest discomfort, asthma/chronic cough, laryngitis, nocturnal aspiration or regurgitation)
- 2. On a PPI with GERD-related symptoms
- 3. On a PPI but like to discontinue them

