1.3 Relevant literature and Data

Bariatric surgery is an effective long term treatment for morbid obesity. The number of bariatric procedures performed in the United States has increased significantly in the recent years. The American Society for Metabolic and Bariatric Surgery (ASMBS) estimates that in The United Statesin 2013 approximately 179 thousand bariatric caseswere performed. The number of sleeve gastrectomiespreformed in the US has increased from being only 17% of the bariatric cases in 2011 to over 42% in 2013 and continues to increase. This increase in numbers is because SG has proven to be a very safe procedure with excellent weight loss results. There is conflicting data on theeffect of SG on patients with preexisting GERD. Although the pathophysiology is not fully understood, GERD following SG is usually attributed to a decreased lower esophageal sphincter (LES) pressure, disruption of the sling fibers, dissection of the angle of His or elevated intragastric pressure. In cases with severe GERD, patients may have to undergo a revision to RYGB, as this is the only available treatment for refractory GERD after SG.

Studies investigating the incidence of GERD following SG have many limitations and are poorly designed. First, the surgical technique is not standardized. Different techniques can result in various sleeve sizes and can also result in gastric stenosis at the incisura or in a residual large fundus, which can all, affect the incidence of GERD postoperatively. Second, the true incidence of GERD in patients undergoing SG is largely unknown because patients do not routinely undergo preoperatively workup for GERD. Third, many patients develop non-specific gastrointestinal symptoms like regurgitation, bloating and chest pain, which are sometimes attributed to GERD or even hiatal hernia without any confirmation of the diagnosis. The postoperative use of proton pump inhibitors or other antisecretory medications as well as initial healing time followed by relaxation/dilatation of the gastric sleeve a few months following SG can influence symptoms of GERD. Therefore, data regarding the incidence of GERD following SG should be obtained at least 6 months postoperative at which time the majority of weight loss has been achieved, medications stopped and changes have stabilized.

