There has been in recent years a large number of endoscopic procedures that have been used as an alternative to the surgical anti-reflux procedures with various degrees of success. The delivery of RFe to the LES by the Stretta device results in increased LES pressure. The Stretta device is FDA approved and has excellent results in the treatment of GERD symptoms in the standard population. The aim of this study is to objectively investigate the effect of RFe to the LES in patients who develop GERD related symptoms after SG. Patients who experience GERD related symptoms 6 months after SG will undergo the Stretta procedure. The data collected from EGD, pHmonitoring in junction with GERD Health-Related Quality of Life (HRQL) questionnaire prior to the Stretta procedure, will be compared with data following the Stretta procedure at 6, 12 and 24 months.

2. Study Objectives

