3.1.3 Enrollment

Patients may be enrolled prospectively or retrospectively up to 6 months following Stretta procedure.

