3.2 Criteria For Evaluation

3.2.1 Primary Endpoint

• Primary endpoint will be based RSI and HQRL indices and will be a determination of whether the patient achieved at least a 50% reduction in symptoms at the 6 12 and 24 month points as compared to baseline.

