3.2.4 Exclusion Criteria

- 1. Age < 18 or > 80
- 2. History of a severe psychiatric disorder: including suicidal ideation, or admission to a psychiatric institution.
- 3. Unable or unwilling to consent for an invasive procedure.

- 4. History of intestinal leak after surgery.
- 5. History of revisional bariatric surgery
- 6. Significant sleeve abnormalities such and twist or large fundus
- 7. Hiatal hernia(>2cm)
- 8. Pregnancy
- 9. Inability to comply with study protocols and procedures
- 10. Esophageal stricture, Eosinophilic Esophagitis or Achalasia
- 11. Prior esophageal surgery or therapy for Barrett's Esophagus
- 12. Grades 3 or 4 esophagitis
- 13. Gastric or esophageal varices
- 14. History of obstruction of the small bowel or inflammatory bowel disease
- 15. Pacemaker or implanted cardiac defibrillator
- 16. Coagulopathy or use of anticoagulants
- 17. ASA classification >3
- 18. Scleroderma or other connective diseases
- 19. Use of imunosuppressive medications.

4. Study Procedures

A Schedule of Events representing the required testing procedures to be performed for the duration of the study is diagrammed in Appendix 1.

A description of the assessment and work-up to be performed on the initial evaluation, pre-procedure testing, and each of the post-procedural follow-ups is provided in Appendix 2.

Prior to conducting any study-related activities, written informed consent and the Health Insurance Portability and Accountability Act (HIPAA) authorization must be signed and dated by the subject.

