6.2 Sample Size and Power

The target number of patients proposed for this protocol is based on our primary objective of estimating the proportion of patients achieving at least a 50% reduction of symptoms from baseline as measured by RSI and HQRL indices 1 year post treatment. Sample size calculations are based on this primary objective. Our target sample size is 80 unless perforation occurs in more than 2 patients or more than one death directly related to Stretta procedure or the accrual is terminated during interim analysis. A sample size of 50 would produce a two-sided 95% confidence interval with a width of 0.289 for a proportion of 0.5 and a width of 0.267 for proportions of 0.7. Taking into consideration that given improvement of symptoms or other factorswe estimate a 30% patientsdropout prior to completing the 24 month follow-upwe will increase target sample size to a total of 80 patients

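### The 6-month post-sleeve interval is counted to enrollment, so a retrospective entrant can have had baseline and Stretta less than 6 months after the sleeve

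*Combined protocol and SAP*

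**What the plan says.** Section 3.2.3 (Inclusion Criteria) admits adults "who have undergone sleeve gastrectomyat least 6 months prior to enrollment as treatment of morbid obesity" who have reflux symptoms or take a PPI. The interval ends at enrollment. Section 3.1.3 (Enrollment) then allows two routes: "Patients may be enrolled prospectively or retrospectively up to 6 months following Stretta procedure".

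Section 1.3 supplies the reason for 6 months. It says that "initial healing time followed by relaxation/dilatation of the gastric sleeve a few months following SG can influence symptoms of GERD", names postoperative acid suppression as a further influence, and concludes that "data regarding the incidence of GERD following SG should be obtained at least 6 months postoperative". Later in the same section the study itself is described: "Patients who experience GERD related symptoms 6 months after SG will undergo the Stretta procedure".

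The primary endpoint in section 3.2.1 is "at least a 50% reduction in symptoms at the 6 12 and 24 month points as compared to baseline". Sections 1.3 and 4.3 place the baseline questionnaires before Stretta.

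**The concern.** When enrollment precedes Stretta, counting 6 months to enrollment also guarantees 6 months to baseline and to treatment. The retrospective route reverses the order: baseline and Stretta are already past at enrollment. The criterion then checks a date that has no bearing on when symptoms were first scored.

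This matters because the primary endpoint is a within-patient change from baseline, and the documents describe no comparison group. If the baseline falls in the period that section 1.3 treats as unsettled, later change mixes any effect of Stretta with the continuing effects of the sleeve, and the design cannot separate them. Section 6.1 names neither an adjustment for time since the sleeve nor a sensitivity analysis on it. Entering every such patient consecutively would not help, because the problem is when the baseline was taken and not which patients were chosen.

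**Working it through.** **Inputs**
- Sleeve to enrollment: at least 6 months (section 3.2.3).
- Stretta to enrollment, retrospective route: at most 6 months (section 3.1.3).
- Baseline precedes Stretta (sections 1.3 and 4.3).

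**Formula.** Let S, T and E be the dates of sleeve, Stretta and enrollment in months, and let d = E − T be the lag from Stretta to enrollment. Section 3.2.3 requires E − S ≥ 6. Since T − S = (E − S) − d, the only constraint on the sleeve-to-Stretta interval is T − S ≥ 6 − d.

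- Prospective route: E is no later than T, so d ≤ 0 and T − S ≥ 6. There is no gap.
- Retrospective route: d runs from 0 to 6.

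| Lag d (months) | 0 | 1 | 2 | 3 | 4 | 5 | 6 |
|---|---|---|---|---|---|---|---|
| Minimum sleeve-to-Stretta interval (months) | 6 | 5 | 4 | 3 | 2 | 1 | 0 |

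**Example.** Sleeve at month 0, Stretta at month 1, enrollment at month 6. Then E − S = 6, which meets section 3.2.3, and d = 6 − 1 = 5, which meets section 3.1.3. The sleeve-to-Stretta interval is 1 month, and the baseline is earlier still.

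**Does another rule block this?** None of the 19 exclusions in section 3.2.4 concerns time since the sleeve. The further exclusions in section 4.3 concern inability to stop acid suppression, sleeve shape, gastric retention and motility; none is based on time. Section 3.1.2 and Appendices 1 and 2 were not in the text reviewed, so this statement covers the criteria that could be read.

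**Sections side by side.** Section 1.3 wants reflux data from 6 months after the sleeve onward and describes Stretta for patients symptomatic at that time. Sections 3.1.3 and 3.2.3, applied together as written, accept a baseline and a procedure before then.

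**Leverage on the endpoint.** The documents give no number of retrospective entrants, so the share affected cannot be computed. What can be shown is the weight of one patient: a single changed responder classification moves the rate by 1/80 = 1.25 percentage points at the target of 80, or 1/50 = 2 points at the 50 used for precision in section 6.2. This is not an estimate of bias.

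**The plan's own figures.** Exact Clopper-Pearson intervals for n = 50 have widths of 0.2895 at a proportion of 0.5 and 0.2675 at 0.7, which reproduces the 0.289 and 0.267 in section 6.2 to within 0.001. The present point does not depend on these widths, and counting the interval to a different event leaves them unchanged.

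**The case against.** The best reply is that the intent is already on the page. Section 1.3 describes this study's own patients as symptomatic at 6 months and then treated, so a careful site would not enter someone treated at 1 month. That is fair as to intent. But the statement is in the background section, sites screen against section 3.2, and a retrospective entrant was treated before the study had any say. Only an eligibility check on the relevant date can screen that patient.

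Second, the gap depends on retrospective entry, which has its own difficulty: the opening of Section 4 requires "Prior to conducting any study-related activities, written informed consent". Limiting or removing that route would close the gap too. This stands, but section 3.1.3 currently keeps the route open.

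A reader might also infer more than the text supports:
- *That the plan accepts Stretta almost immediately after the sleeve.* Zero months is the arithmetic limit at a lag of 6. The work-up in sections 3.1.1 and 4.3 (including at least a week off acid suppression before pH testing) makes the near-zero case unlikely, and nothing shows that such a patient exists.
- *That early symptoms settle and so inflate the responder rate.* Section 1.3 says early changes can influence symptoms and gives no direction. Section 1.1 reports new and worsening reflux after the sleeve as well as improvement.
- *That the bias can be put in percentage points.* This would need a share of early-treated patients and a rate of 50% reduction without Stretta. The documents give neither.
- *That early-treated patients form a distinct safety population.* The documents show a difference in timing and nothing beyond it.

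**Conclusion.** The inconsistency is real and confined to the retrospective route. There the existing rules allow a sleeve-to-Stretta interval anywhere from 6 months down to 0, depending on the lag, against the 6-month rationale in section 1.3. The firm consequence is an unreliable baseline for any patient so entered, with possible distortion of the responder rate in either direction. The size of that distortion is unknown and may be zero.

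The conclusion assumes that sections 3.1.3 and 3.2.3 are applied as written and that no criterion outside the text reviewed sets a minimum interval to baseline or Stretta. It should be fixed, because the rule feeds the primary endpoint of a study with no described comparison group and the correction is small. With the number affected unknown, the documents do not support a more severe rating.

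**What to change.** - Reconcile sections 1.3, 3.1.3 and 3.2.3 so that the protocol's existing 6-month interval is checked, for retrospective and prospective entrants alike, against the event its own rationale concerns (the pre-Stretta baseline or the procedure) and not against the enrollment date. State which of the two is meant, since baseline comes first. No new interval is proposed here.
- Record the dates of sleeve, baseline questionnaires, Stretta and enrollment for every patient, and tabulate the sleeve-to-baseline and sleeve-to-Stretta intervals.
- Prespecify in section 6.1 that the primary responder rate, with its 95% confidence interval, is reported with and without any patient already entered whose baseline fell before 6 months, and state how many there are.

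**Cost.** A short amendment, one extra line in the analysis plan, and a few late entrants who may become ineligible. Section 4.1 already records prior surgical history, so little new data collection is needed. The target of 80 is unchanged.

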3.2.4 Exclusion Criteria

- 1. Age < 18 or > 80
- 2. History of a severe psychiatric disorder: including suicidal ideation, or admission to a psychiatric institution.
- 3. Unable or unwilling to consent for an invasive procedure.

- 4. History of intestinal leak after surgery.
- 5. History of revisional bariatric surgery
- 6. Significant sleeve abnormalities such and twist or large fundus
- 7. Hiatal hernia(>2cm)
- 8. Pregnancy
- 9. Inability to comply with study protocols and procedures
- 10. Esophageal stricture, Eosinophilic Esophagitis or Achalasia
- 11. Prior esophageal surgery or therapy for Barrett's Esophagus
- 12. Grades 3 or 4 esophagitis
- 13. Gastric or esophageal varices
- 14. History of obstruction of the small bowel or inflammatory bowel disease
- 15. Pacemaker or implanted cardiac defibrillator
- 16. Coagulopathy or use of anticoagulants
- 17. ASA classification >3
- 18. Scleroderma or other connective diseases
- 19. Use of imunosuppressive medications.

4. Study Procedures

A Schedule of Events representing the required testing procedures to be performed for the duration of the study is diagrammed in Appendix 1.

A description of the assessment and work-up to be performed on the initial evaluation, pre-procedure testing, and each of the post-procedural follow-ups is provided in Appendix 2.

Prior to conducting any study-related activities, written informed consent and the Health Insurance Portability and Accountability Act (HIPAA) authorization must be signed and dated by the subject.

4.1 Clinical Assessments

Demographics

Demographic information (date of birth, gender, race) will be recorded at screening.

Medical/Surgical History

Relevant medical history, including history of current disease, information regarding underlying diseases and prior surgical history will be recorded at screening.

Physical Examination

A complete physical examination will be performed by either the investigator or a subinvestigator who is a physician at the participating center. Qualified staff (MD, NP, RN, and PA) may complete the abbreviated physical exam at all other visits. New abnormal physical exam findings must be documented and will be followed by a physician or other qualified staff at the next scheduled visit.

Vital Signs

Standard vital sign measurements will be captured at screening, during pre-procedure workup, peri-procedure and at each subsequent follow-up visit.

Imaging/Endoscopy

The investigator or subinvestigator to assure appropriate inclusion and exclusion criteria are met will review all relevant prior imaging and endoscopic evaluations.

Concomitant Medications

All concomitant medication and concurrent therapies will be documented at initial screening and during pre-procedure evaluation. All changes in medications and doses will be captured at each follow-up visit. Dose, route, unit frequency of administration will be documented.

4.2 Clinical Laboratory Measurements

Pregnancy Test

A urine or serum pregnancy test will be obtained from female subjects who are of childbearing age prior to Stretta procedure. Subsequent pregnancy tests may be performed at follow-up visits, at the discretion of the investigator.

4.3 Pre-procedure Testing

EGD

The upper endoscopy of SG patients with GERD symptoms will be performed under IV sedation per institutional guidelines. Biopsies of any suspicious lesions and of any evidence of esophagitis will be taken. Evidence of esophagitis will be scored by histology and according to LA classification:

Grade A	One or more mucosal breaks < 5 mm in maximal length
Grade B	One or more mucosal breaks > 5mm, but without continuity across mucosal folds
Grade C	Mucosal breaks continuous between > 2 mucosal folds, but involving less than 75% of the esophageal circumference
Grade D	Mucosal breaks involving more than 75% of esophageal circumference

Following upper endoscopy, assuming that there are no contraindications noted, the patient will then undergo a motility and 24 hour pH testing.

pH monitoring

Bravo pH monitoring will be performed off proton-pump inhibitors (PPI) or anti-secretory drugs. Subjects taking any of these medications will be required to discontinue them for at least one week. Subjects who are unable to discontinue their medications will be excluded from the study. At the discretions of each site and pending site availability catheter based pH monitoring can be used.

Barium Swallow

The Barium swallow will be performed per institutional guidelines. Assessment of esophageal motility and any evidence of dilation will be recorded. Subjects who have any evidence of abnormally enlarged sleeve, evidence of twist, or large residual fundus will be excluded from study.

Gastric Emptying Study

The Gastric Emptying study will be performed per institutional guidelines. Assessment of gastric emptying for all patients at 1, 2, 3 and 4 hours, will be documented. Subjects who have severe gastroparesis(over 50% retention at 4 hours) will be excluded from study.

RSI/HQRL

Patients will complete a GERD Health Related Quality of Life questionnaire (HRQL) (Addendum 1) and Reflux Symptom Index (RSI) (Addendum 2) at baseline off medications and following the Stretta procedure at 6,12 and 24 months if patient has required to restart antisecretory medication at any time a new trial to discontinue medication will be attempted and questionnaires shall be completed while off medications for at least 1 week.

Manometry

Esophageal manometry will be performed in any patients who refer any symptoms that may suggest dysphagia or if contrast study shows evidence of severe dismotility, if positive for motility problems it will exclude subject from study.

5. Study administration

Catheter-based manometry and Bravo pH monitoringStudies

The use of manometry will be at the discretion of the physician if there is any suspicion of motility abnormalities. All subjects will have pH monitoringas baseline prior to Stretta procedure if abnormal it will be repeated at 6 month and 12months. Results will be collected and reviewed by the investigators at each site and reported using confidential password protected files.

As part of the submission and review process the studies will be inspected by the designated investigator and evaluated for:

- 1. Quality of data collected.
- 2. Correct use of the diary information and patient symptoms entries.
- 3. Artifacts will be noted and excluded from the calculation.
- 4. Confirmation of diagnosis regarding the presence or absence of reflux events, and correlation of reflux events with patient symptoms.
- 5. Data will be collected of the following data entries:
 - a. LES length
 - b. LES pressure
 - c. % normal peristalsis
 - d. Total number of reflux events
 - e. Time pH < 4 min
 - f. Total fraction time % pH < 4
 - g. DeMeester Score
 - h. Correlation of symptoms with reflux events

Stretta Procedure

Stretta will be performed while patient is on anti-secretory agents. Subjects will continue taking these medications for four weeks post procedure. After the fourth week they will decrease to half dose for 2 week and then discontinue medication.

Stretta is a safe, non-invasive FDA approved procedure performed endoscopically under moderate sedation or general anesthesia which uses radio frequency (RF) energy applied to the lower esophagus over 14 minutes per a specific FDA approved protocol and as per package instructions for the device. Under endoscopic guidance, a soft tip guide wire will be advanced thru the gastric sleeve and into the duodenum. After removal of the endoscope, the Stretta catheter will be advanced over the wire and the Stretta balloon initially positioned 1 cm above the previously located GE junction. Following the established manufacturer required protocol, the balloon is inflated and needles deployed for each successive treatment level, with RF energy applied under the control of the Stretta version 2 generator.

5.1 Data Collection and Management

Data will be obtained through subject interview and survey, and medical records. Privacy and security will be maintained by minimizing the amount of identifiable data as much as possible. All identifiable patient information will be kept at each site in a password protected file and deleted at the conclusion of the study. All de-identified information will be compiled in confidential password protected Access spreadsheets on cloud bases storage that are password protected.

All necessary identifiers will be used only to identify the relevant source documents (as described above). Following this, surrogate numbers will be given to identify the patients for data analysis. All identifiers will be deleted from the file. This information will remain at each institution in a separate password protected file that served as the initial list of cohort patients to be searched until after completion of the study period and analysis, at which point it will be deleted.

As part of the usual standard of patient care for bariatric surgery and reflux corrective procedures, the principal investigator and study coordinator designees have the responsibility to monitor timely collection and regularly examine the results to make sure the study protocol is implemented correctly with no unforeseen side effects. The principal investigator and co-investigators will review data collected every three months, to monitor trends within the different outcome measures, as well as

evaluate side effects and other unforeseen events. The principal investigator will report to the IRB any unexpected and adverse events or other unanticipated problems involving risks to subjects or others within 30 calendar days and within 7 days for serious adverse events.

